Participants will be provided with instructions on the use of the eDiary to complete when they experience qualifying prodrome events and they will be made aware of timepoints as to when

they are expected to enter data in the eDiary. A practice session with a hypothetical scenario should be administered to ensure the participants' comprehension of the questions and the information to be entered. In addition, criteria for qualifying prodrome events to be treated as well as prohibited medications should be reviewed with the participants. Participants should receive instructions on how to take the study intervention, the criteria for a qualifying prodrome event, and when participants are allowed to take rescue medication. Participants will be instructed to bring their eDiary at the next study visit and return their study intervention (used and unused).

For participants participating in the optional PK substudy, DBS sample collection training will be provided at Visit 2. For participants who have successfully completed the collection training, participants will be provided with the PK collection supplies and provided instructions on when the DBS samples must be collected and the dates and times recorded in the eDiary. Participants will collect 3 DBS samples at home after treating each qualifying prodrome event and record the date and time in their eDiary. Collection times are outlined in Section 8.5.

8.1. Efficacy Assessments

Efficacy measurement assessments are based on information recorded by the participant in an eDiary.

Absence/Presence of and Rating of Intensity of Prodrome Symptom(s)

After experiencing each qualifying prodrome event, the absence or presence of each identified prodrome symptom(s) will be followed (up to 48 hours) and the intensity subjectively rated (mild, moderate, or severe) for those that are present.

Absence/Presence of Headache and Rating of Headache Intensity

After the prodrome symptoms have started, the participant will be alerted to record the presence of a headache when it occurs or record the absence/presence at various timepoints (up to 48 hours) following the dose of double-blind study intervention (during the double-blind treatment period). If a headache is reported as present, the intensity will be subjectively rated (mild, moderate, or severe).

Absence/Presence of and Rating of Intensity of Nonheadache Symptoms

The participant will record whether nonheadache symptoms (photophobia, phonophobia, nausea, and/or dizziness) were absent or present as well as the intensity (mild, moderate, or severe) of the present nonheadache symptom (up to 48 hours).

50

Absence/Presence of Aura

The participant will record whether aura was present or absent (up to 48 hours).

Health outcomes assessments are described in Section 8.10.

8.2. Safety Assessments

Planned timepoints for all safety assessments are provided in the SoA (Section 1.3).

8.2.1. Physical Examinations

A complete physical examination will be performed at the visits outlined in SoA (Section 1.3).

- A professionally trained physician or healthcare professional licensed to perform physical examinations will examine the participant for any detectable abnormalities of the following body systems: general appearance; neck (including thyroid); head, eyes, ears, nose, and throat; lungs; heart/cardiovascular; abdomen; neurologic; extremities; back; musculoskeletal; lymphatic; skin; and other.
- The neurologic examination should be conducted to detect the presence of any significant sensory/motor abnormalities.

8.2.2. Vital Signs

Vital sign measurements, including sitting and standing BP, sitting and standing pulse rate, respiratory rate, temperature, body weight, and height (at Visit 1 only), will be performed at every visit.

Sitting and standing BP and pulse rate will be determined as follows: BP and pulse measurements will be performed after the participant sits quietly for 5 minutes, followed by a second set of measurements taken after the participant stands for 3 minutes (but no longer than 10 minutes).

8.2.3. Electrocardiograms

A 12-lead ECG will be performed at the visits outlined in the SoA (Section 1.3). Only one ECG is required for each assessment at each specified visit. All ECGs should be performed after the participant has been supine for at least 5 minutes. A copy of the ECG will be saved as a source document. ECGs will be transmitted electronically to the central ECG laboratory for analysis according to the instructions provided by the laboratory to be read by a cardiologist. If multiple ECGs are completed, all ECGs (readable and unreadable) must be transmitted to the central ECG vendor. The overall interpretation of the clinical significance of the ECGs will be determined by the investigator and recorded in the source notes.

8.2.4. Clinical Safety Laboratory Assessments

- See Section 10.2 for the list of clinical laboratory tests to be performed and the SoA (Section 1.3) for the timing and frequency. Hematology, chemistry, urinalysis, and urine pregnancy tests will be conducted at the Screening Visit (Visit 1), Randomization Visit (Visit 2), and Posttreatment/ET Visit (Visit 4). Coagulation, and the urine drug screen will be conducted at the Screening Visit (Visit 1) only.
- The investigator or subinvestigator will assess the clinical significance of any values outside the reference ranges provided by the laboratory, and participants with abnormalities judged to be clinically significant will be screen failed or withdrawn from the study.

- Positive results on the urine drug screen (unless explained by previously reported concomitant medication use, such as opioids prescribed for migraine pain) will be excluded from the study.
- A positive pregnancy test at Visit 1 or Visit 2 will exclude the participant from participation in the study. Participants who are confirmed to be pregnant during the study will be withdrawn.
- The investigator must review the laboratory report, document this review, and record any clinically relevant changes occurring during the study in the AE section of the eCRF. The laboratory reports must be filed with the source documents. Clinically significant abnormal laboratory findings are those that are not associated with the underlying disease, unless judged by the investigator to be more severe than expected for the participant's condition.
- All laboratory tests with values considered clinically significant during participation in the study or within 30 days after the last dose of study intervention should be repeated until the values return to normal or baseline or are no longer considered clinically significant by the investigator.
 - If such values do not return to normal/baseline within a period of time judged reasonable by the investigator, the etiology should be identified and the sponsor notified.
 - All protocol-required laboratory assessments, as defined in Section 10.2, must be conducted in accordance with the laboratory manual and the SoA (Section 1.3) or laboratory manual.
 - o If laboratory values from nonprotocol specified laboratory assessments performed at the institution's local laboratory require a change in participant management or are considered clinically significant by the investigator (eg, SAE or AE or dose modification), then the results must be recorded as an SAE or AE in the eCRF.

8.2.5. Suicidal Ideation and Behavior Risk Monitoring

Ubrogepant is considered to be CNS active and participants being treated should be monitored appropriately and observed closely for suicidal ideation and behavior.

The C-SSRS is a clinician-rated instrument that reports the severity of both suicidal ideation and behavior. Suicidal ideation is classified on a 5-item scale: 1 (wish to be dead), 2 (nonspecific active suicidal thoughts), 3 (active suicidal ideation with any methods [no plan] without intent to act), 4 (active suicidal ideation with some intent to act, without specific plan), and 5 (active suicidal ideation with specific plan and intent). The C-SSRS also captures information about the intensity of ideation, specifically the frequency, duration, controllability, deterrents, and reasons for the most severe types of ideation. Suicidal behavior is classified on a 5-item scale: 0 (no suicidal behavior), 1 (preparatory acts or behavior), 2 (aborted attempt), 3 (interrupted attempt), and 4 (actual attempt). More than 1 classification can be selected provided they represent separate episodes. For actual attempts only, the actual or potential lethality is classified for the initial, most lethal, and most recent attempts.

The C-SSRS will be completed at all study visits. At the Screening Visit (Visit 1) the C-SSRS will be completed for the participant's lifetime history and 6 months of suicidal ideation and suicidal behavior to assess eligibility. Based on this assessment and investigator judgment, if there is significant risk of self harm or harm to others, the participant must be excluded from the study. At all other visits, the C-SSRS will be completed for ideation and behavior since the previous visit.

The C-SSRS will be completed on the eTablet by the investigator or designee with current and valid training in administering the assessment. A participant should not be released from the study center until the results of C-SSRS are reviewed and it is confirmed that the participant is not considered to be at risk.

8.3. Adverse Events and Serious Adverse Events

The definitions of an AE or SAE can be found in Section 10.3.

AEs will be reported by the participant (or, when appropriate, by a caregiver, surrogate, or the participant's legally authorized representative).

The investigator and any qualified designees are responsible for detecting, documenting, and recording events that meet the definition of an AE or SAE and remain responsible for following up AEs that are serious, considered related to the study intervention or study procedures, or that caused the participant to discontinue the study intervention or study (see Section 7).

8.3.1. Time Period and Frequency for Collecting AE and SAE Information

All SAEs and AEs from the signing of the ICF until 30 days after the last dose of study intervention will be collected at the timepoints specified in the SoA (see Section 1.3), and as observed or reported spontaneously by study participants.

Medical occurrences that begin before the start of study intervention but after obtaining informed consent will be recorded in the AE section of the eCRF and will be considered pretreatment AEs.

All SAEs will be recorded and reported to the sponsor or designee immediately and under no circumstance should this exceed 24 hours, as indicated in Section 10.3 (Appendix 3). The investigator will submit any updated SAE data to the sponsor within 24 hours of it being available.

Investigators are not obligated to actively seek AE or SAE information after conclusion of the study participation. However, if the investigator learns of any SAE, including a death, at any time after a participant has been discharged from the study, and he/she considers the event to be reasonably related to the study intervention or study participation, the investigator must promptly notify the sponsor.

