This visit will occur 4 days (-2/+4 days) after double-blind study intervention is taken for the second qualifying prodrome event. It can occur as early as 2 days after taking double-blind study intervention (after the 48 hour assessment has been completed) and as late as 8 days after taking double-blind study intervention; however, participants should be encouraged to come in for this visit as soon as possible after completing their 48 hour assessments.

If none or 1 qualifying prodrome event has been treated during the double-blind treatment period and the 60-day time period has ended, the site will call the participant to schedule an ET Visit.

Randomized participants who exit the study early for any reason, whether or not they have taken study intervention, should also receive these evaluations. The following study procedures will be carried out at the Posttreatment/ET Visit (Visit 4):

- Register the participant's visit in the IWRS
- Collect vital sign measurements (sitting and standing systolic and diastolic BP, sitting and standing pulse rate, respiration rate, temperature, and weight)
- Review concomitant medication
- Review and assess AEs
- Assess C-SSRS on eTablet (the Since the Last Visit assessment of the C-SSRS will be completed)
- Perform ECG
- Perform physical examination
- Collect blood and urine samples for clinical laboratory tests (chemistry, hematology, and urinalysis)
- Perform urine pregnancy test (for WOCBP only)
- Collect eDiary and ensure all recorded data has been sent
- Review eDiary entries and ensure all questions and assessments were completed
- Collect side effects diary. Review the side effects listed on the diary and enter identified AEs in EDC.
- Collect study intervention blister package; review compliance against the information collected in the eDiary

For those participants participating in the optional PK substudy:

• Collect the DBS samples that the participant collected at home and ensure that the collection dates and times are recorded in the eDiary

Unscheduled Visits

Additional examinations, laboratory assessments, and pregnancy tests may be performed as necessary to ensure the safety and well-being of the participants during the study. Unscheduled visit eCRFs should be completed for each unscheduled visit.

Instructions for Participants

Section 5.3.1, Section 5.3.2, and Section 5.3.3 list dietary restrictions and activity instructions for participants enrolled in the study.

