### **9.2.3 Treatment-Emergent Adverse Events by SOC and/or PT**

AEs will primarily be assessed through the analysis of AEs reported in the 48 hours following the administration of each study intervention. A supportive analysis will include AEs reported within 30 days after the study intervention (and before the next intervention if any). Unique participants reporting AEs will be summarized in the following AE categories by treatment and total for the safety population in double-blind treatment period.

- TEAEs by SOC and PT.
- TEAEs by SOC, PT and severity. If more than 1 AE is coded to the same PT for the same participant, the participant will be counted only once for that PT using the maximum severity for the summarization by severity. If the severity of a TEAE is missing, the maximum severity will be assigned to the event for the summarization by severity. The value will be displayed as missing in the data listing.
- Treatment-related TEAEs by SOC and PT. If more than 1 AE is coded to the same PT for the same participant, the participant will be counted only once for that PT using the closest causal relationship to treatment for the summarization by causal relationship. If the relationship to the study intervention is missing for a TEAE, the event will be considered related to the study intervention for the summarization. The value will be displayed as missing in the data listing.
- The incidence of common ( $\geq 2\%$  [after rounding] of participants in either study intervention) TEAEs will be summarized by descending frequency in the ubrogepant group.

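### AE collection and analysis are stated to day 30 after dosing, but after the second dose the last scheduled contact is on day 2 to 8, so the supportive AE percentages are not complete 30-day incidence.

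*Protocol*

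**What the plan says.** Protocol 8.3.1 sets the collection window: "All SAEs and AEs from the signing of the ICF until 30 days after the last dose of study intervention will be collected". The same sentence gives the means: "at the timepoints specified in the SoA (see Section 1.3), and as observed or reported spontaneously by study participants". Later in that section: "Investigators are not obligated to actively seek AE or SAE information after conclusion of the study participation".

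The last column of the Schedule of Activities (Protocol 1.3) is Visit 4/ET. Protocol Section 8 lists four clinic visits and one phone call, and the call falls in screening. On Visit 4 it says: "This visit will occur 4 days (-2/+4 days) after double-blind study intervention is taken for the second qualifying prodrome event". The visit may be as early as day 2 "and as late as 8 days after taking double-blind study intervention", and "participants should be encouraged to come in for this visit as soon as possible after completing their 48 hour assessments". The paper side-effects diary covers the 48 hours after each dose. Under Protocol 4.4, a participant completes the study with the last visit or last scheduled procedure.

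On the analysis side, Protocol 9.4.2.1 and SAP 9.2.1 stop counting an event as treatment-emergent once it begins more than 30 days after the dose concerned. AEs are assessed primarily over 48 hours. SAP 9.2.3 then adds: "A supportive analysis will include AEs reported within 30 days after the study intervention", cut off at the next dose where there is one. Neither document asks for follow-up time in the AE tables.

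**The concern.** Protocol 8.3.1 commits to 30 days of collection after the last dose, while the visit schedule and the wording on investigators' duties end active inquiry within about a week. The analysis sections take the 30-day window at face value. Readers of the supportive table may treat it as the proportion of participants with an event in the 30 days after ubrogepant or placebo, and may take few late events as evidence that few occurred, when no one was scheduled to ask. Two things are at stake: the absolute percentages in that table, and an accurate statement of how long participants were followed for safety after the second dose.

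**Working it through.** **Inputs**

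- Stated window: 30 days after dose (Protocol 8.3.1 and 9.4.2.1; SAP 9.2.1 and 9.2.3).
- Visit 4: day 4 after dose 2, window -2/+4 (Protocol 1.3 and Section 8).
- Primary AE window: 48 hours, that is 2 days (Protocol 9.4.2.1; SAP 9.2.3).
- Minimum gap between doses: 7 days (Protocol 4.1 and Section 8).
- Allocation: 1:1, 258 per sequence (Protocol 1.1).

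**Step 1. Reproduce the plan's visit range.** 4 - 2 = 2 and 4 + 4 = 8, which agrees with the stated range of 2 to 8 days.

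**Step 2. Period 2 days with no scheduled contact.** Days = 30 - d, share = (30 - d)/30, where d is the day of Visit 4.

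| Visit 4 on day | Days without scheduled contact | Share of 30 days |
|---|---|---|
| 2 | 28 | 93% |
| 4 (nominal) | 26 | 87% |
| 8 | 22 | 73% |

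**Step 3. What the supportive analysis adds in Period 2.** It extends the 48-hour analysis by 30 - 2 = 28 days. Scheduled contact covers d - 2 of them: 0 of 28 (d = 2), 2 of 28 = 7% (d = 4) or 6 of 28 = 21% (d = 8).

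**Step 4. Period 1.** Participants who take a second dose and attend Visit 4 have a further AE review after the whole interval between doses. The active window therefore runs from dose 1 to dose 2: at least 7 days, and at most 30 because of the analysis limit. Set against 2 to 8 days in Period 2, the windows are nearly equal at one extreme (7 against 8) and far apart at the other (30 against 2).

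**Step 5. Pooling by treatment.** Suppose everyone takes both doses and attends Visit 4. Each treatment then has 258 exposures in each period, and its average active window is (Period 1 + Period 2)/2. That lies between (7 + 2)/2 = 4.5 days and (30 + 8)/2 = 19 days, against the nominal 30. Under this assumption the structure is the same for both treatments, so any shortfall falls on both alike.

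**The case against.** The strongest reply is that the window after Visit 4 is not empty. Protocol 8.3.1 itself provides for observed and spontaneously reported events. Section 8 allows unscheduled visits. Section 8.2.4 requires clinically significant laboratory values arising within 30 days of the last dose to be repeated. Section 8.3.3 follows SAEs and AEs of special interest to resolution, and Section 9.4.2.6 includes unscheduled laboratory results after Visit 4 in the Hy's Law analysis. All of this stands. A reader might infer that nothing is observed after Visit 4, and the documents do not support that. These routes are passive or triggered, however, so they cannot give complete capture to day 30.

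Second, 30 days is written as an outer limit for counting events, with truncation at the next dose stated openly; neither document calls the result a 30-day incidence. That is true, and the concern is how the table will be read when it carries no follow-up time.

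Third, the consequence is limited. This is a single dose with effective concentrations put at about 15 hours (Protocol 2.1), and the primary AE window of 48 hours is covered by the diary and reviewed at Visits 3 and 4. This also stands. A reader might turn the uncovered days into a share of events missed, but that needs a constant event rate over 30 days and no reporting after Visit 4. The documents give no support for the first and contradict the second. The day counts are supported; a captured share of events is not.

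**Conclusion.** The text is wrong as written: the schedule does not deliver the active 30-day collection that the stated windows imply. For participants who take a second dose, 22 to 28 of the 30 days that follow (73% to 93%) are not actively ascertained. Period 1 is actively ascertained up to the second dose, so the supportive table pools unequal windows, and its percentages are not complete 30-day incidence.

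The finding has limits. The 2-to-8-day figure applies to participants who take a second dose. Those who treat only one event and reach the end of the 60 days have an ET visit that may fall beyond day 30 after their dose. The primary 48-hour analysis is unaffected. A reader might infer a bias between treatments, but each treatment is given in each period to about half of the participants, so the comparison is approximately balanced. It is not exactly so, because dropout after the first dose and the time to the second dose may vary. The size of any undercount of events cannot be derived from the documents. The point should be corrected, but it does not threaten the efficacy result or the main safety comparison.

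**What to change.** Reconcile Protocol 1.3, Section 8 (Visit 4), 8.3.1 and 9.4.2.1 with SAP 9.2.1 and 9.2.3, so that the stated collection and analysis windows match the schedule. The length of follow-up is for the sponsor to decide.

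If the schedule stays as it is:

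- State in Protocol 8.3.1 that active ascertainment ends at Visit 4/ET, with passive reporting to day 30, and carry this into the analysis sections.
- Keep every reported treatment-emergent event in the supportive table.
- Add a row of actively ascertained participant-days by treatment and period. Count from dose to the earliest of the next dose, day 30, and the last visit or contact at which AEs were reviewed. An exposure-adjusted rate would also serve, if its numerator is limited to events with onset in those days.
- Add a note that the percentages are not complete 30-day incidence.

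Shortening the supportive window to run from dose to posttreatment visit would not be a good substitute. It would discard Period 1 events between Visit 3 and the second dose, which Visit 4 reviews, and would still vary from 2 to 8 days.

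The cost is wording changes in both documents, one extra row and a footnote in the AE tables, and a less favourable statement of how long safety was followed.

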8.3.2. Method of Detecting AEs and SAEs

The method of recording, evaluating, and assessing causality of AEs and SAEs and the procedures for completing and transmitting SAE reports are provided in Appendix 3.

Care will be taken not to introduce bias when detecting AEs and/or SAEs. Open-ended and nonleading verbal questioning of the participant is the preferred method to inquire about AE occurrences.

